1.0 Objectives

1.1 Study Objectives

Describe the purpose, specific aims or objectives. State the hypotheses to be tested.

This pilot study seeks to determine if formula feeding recommendations that are calibrated using age and weight specific caloric intake recommendations can prevent excessive infant weight gain and reduce overweight in the first 6 months after birth among infants born to mothers with overweight prior to pregnancy electing to exclusively formula feed their infants. Calibrated formula feeding refers to adjusting the recommended daily caloric formula intake to account for weight status. A cohort of 60 infants will be recruited and randomized 2-3 weeks after birth to an intervention arm characterized by calibrated formula feeding recommendations or a control group with ad lib feeds as per usual care. Intervention group parents will also be given written instructions on infant hunger and satiety cues as well as copies of videos with guidance on bottle feeding and how to soothe fussy infants without feeding. We hypothesize that the calibrated formula intake intervention will reduce rapid infant gain and overweight during infancy resulting in lower weight-for-length at age 6 months.

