3.1 Inclusion Criteria

Create a numbered list of the inclusion criteria that define who will be included in your final study sample (e.g., age, gender, condition, etc.)

1. Term or Early Term (≥ 37 weeks), singleton infants
2. Infant birthweight $\geq 50^{\text{th}}$ percentile based on the 2013 Fenton Growth Charts (which account for sex of child and gestational age at birth)
3. Infant without substantial neonatal morbidity that would affect feeding or weight gain (e.g. known chromosomal abnormality, metabolic disorder, cleft lip/palate, etc.)
4. Infant age ≤ 1 month
5. Mothers with pre-pregnancy body mass index $\geq 25 \text{ kg/m}^2$
6. Mothers ≥ 18 years old
7. Parental plan to exclusively feed infant 19-20 kcal/ounce formula upon delivery or by the start of the intervention period ~ 1 month after delivery
8. Parental intention to have infant well child visits through age 6 months at a Division of Academic General Pediatrics practice site (Hope Drive, Elizabethtown, Nyes Road)
9. English speaking parent

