3.2 Exclusion Criteria

Create a numbered list of the exclusion criteria that define who will be excluded in your study.

1. Infants who weigh less than their birthweight 21 days after delivery

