4.1 Identification of subjects

Describe the source of subjects and the methods that will be used to identify potential subjects (e.g., organizational listservs, established recruitment databases, subject pools, medical or school records, interactions during a clinic visit, etc.). If not recruiting subjects directly (e.g., database query for eligible records or samples) state what will be queried, how and by whom.

StudyFinder:

- If you intend to use StudyFinder (<http://studyfinder.psu.edu>) for recruitment purposes, include this method in this section.
- Information provided in this protocol needs to be consistent with information provided on the StudyFinder page in your CATS IRB study.

For Penn State Health submissions using Enterprise Information Management (EIM) for recruitment, and for non-Hershey locations as applicable, attach your EIM Design Specification form on in CATS IRB (<http://irb.psu.edu>). See “HRP-103- Investigator Manual, What is appropriate for study recruitment?” for additional information. **DO NOT** include the actual recruitment material or wording in this protocol.

Participants will be identified during the birth hospitalization at Penn State Hershey Children’s Hospital and through newborn visits at a practice site within the Division of Academic General Pediatrics (offices at Hope Drive, Elizabethtown, Nyes Road) via review of birth hospitalization and neonatal electronic medical records.

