7.1 Study Design

Describe and explain the study design.

This study is a randomized, clinical trial involving 60 exclusively formula fed infants born at ≥ 37 weeks gestational age who are at-risk for overweight based upon maternal pre-pregnancy overweight or obesity (or alternatively at first prenatal visit if pre-pregnancy weight/height not known) and infant birthweight $\geq 50^{\text{th}}$ percentile. Infants will be enrolled at Penn State Health Children's Hospital or at affiliated clinics within the Division of Academic General Pediatrics between birth and age 1 month, where they will be randomized to a calibrated formula intake intervention or control. Participating infants in the intervention group will be seen monthly until age 6 months where they will be weighed and measured, and parents will complete surveys related to volume of formula consumed, infant appetite, parent feeding style, and infant temperament. Control infants will follow the same procedures, but will not have scheduled visits at ages 3 and 5 months. Instead their visits will correspond to usual care well child visits at ages 1, 2, 4, and 6 months.

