7.2 Study Procedures

Provide a step by step description of all research procedures being conducted (broken down by visit, if applicable) including such information as below (where and when applicable); describe the following:

- HOW: (e.g., data collection via interviews, focus groups, forms such as surveys and questionnaires, medical/school records, audio/video/digital recordings, photographs, EKG procedures, MRI, mobile devices such as electronic tablets/cell phones, observations, collection of specimens, experimental drug/device testing, manipulation of behavior/use of deception, computer games, etc.)

- WHERE: (e.g., classrooms, labs, internet/online, places of business, medical settings, public spaces, etc.)

Prior to enrollment, infants will be screened by study coordinators to ensure eligibility consistent with study inclusion/exclusion criteria.

7.2.1 Visit 1

Provide a description of what procedures will be performed on visit 1 or day 1 or pre-test in order of how these will be done. If your study only involves one session or visit, use this section only and indicate 7.2.2 as not applicable.

Birth – infant age 1 month: Parents will then review and complete the informed consent document during the birth hospitalization or at a clinic visit allowing for continued participation. Demographic data will be collected from parent-completed surveys on Redcap. Study coordinators will review the electronic medical record to obtain data related to pregnancy and birth history (e.g. birthweight, gestational age, maternal pre-pregnancy BMI, etc.). Additionally, parent contact information will be obtained.

Anthropometrics – if enrollment occurs during the birth hospitalization, birth weight and birth length will be recorded from the electronic medical record. If enrollment occurs at an outpatient clinic visit, the following procedures will be used (and for all subsequent weights and lengths):

- Weight – will be measured to the nearest 0.001 kg using a calibrated, digital electronic scale
- Recumbent Length – will be measured to the nearest 0.1 cm using a portable stadiometer (Shorr)

Diary card - Parents will be given a diary card to record volume of infant formula consumed for the 3 days prior to the 1 month well child visit (Visit 2) and all subsequent visits. Instructions for the diary card will ask parents:

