- a) Volume consumed in each feeding for the day (volume is the amount that passes the infant's lips – if formula is spit-up, it still counts as having been consumed)
- b) Type of infant formula
- c) Size of bottle used
- d) Other sources of nutrition (e.g. juice, water, foods)

Randomization – following the visit, infants will be randomized to intervention or control using a computer-generated randomization program generated by a statistician not affiliated with the trial. Randomization will include stratification for sex of the infant (male/female) and maternal pre-pregnancy BMI category ($25-29.9 \text{ kg/m}^2$ vs. $\geq 30 \text{ kg/m}^2$).

7.2.2 Visit 2

Provide a description of what procedures will be performed on visit 2 or day 2 or post-test in order of how these will be done. If your study involves more than two sessions or visits replicate this section for each additional session or visit (e.g., 7.2.3, 7.2.4, etc.).

Age 1 Month Visit (ages 24 – 41 days)

Both study groups:

1. Anthropometrics of infant (weight, recumbent length)
2. Parent-completed Surveys
 - a. Baby Eating Behavior Questionnaire⁷⁶
 - b. Babies Basic Needs Questionnaire

- c. Single item adapted from the Infant Feeding Practices Study II⁷⁷: “I encourage my infant to finish his or her bottle of formula”⁷⁸; responses include:
Never Rarely Sometimes Most of the time Always.....
- 3. Diary cards to be completed for the 3 days following the visit
- 4. Diary cards to be completed x 3 days prior to next study visit

Intervention group only:

1. Parents will be provided with handouts on hunger/satiety cues and calming a fussy baby
2. Parents will be given a digital streaming copy of the video, “Happiest Baby on the Block” available at: <https://www.happiestbaby.com/products/baby-streaming-video-english>
3. Parents will be given a copy of a video demonstrating responsive bottle feeding: <https://youtu.be/NLnPGJKdPUw>⁷⁸
4. Parents will be given a copy of Bottle Feeding Basics video: <https://360.articulate.com/review/content/99a63b9a-184c-474e-b836-7d8cd8aa1652/review>
5. Study coordinators will provide parents with a range of formula volume to be consumed based upon research conducted by Butte:⁷⁹

Table 8 Energy requirements for formula-fed infants 0–12 months of age

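### Randomisation is allowed before day 21, when the only exclusion criterion can first be assessed, and the plan does not say what happens to a randomised infant who then fails it

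*Combined protocol and SAP*

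**What the plan says.** The only item under Exclusion Criteria (3.2) is "Infants who weigh less than their birthweight 21 days after delivery".

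Randomisation is timed in three places:

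- Section 1.1: infants are "randomized 2-3 weeks after birth".
- Section 7.1: infants are enrolled "between birth and age 1 month, where they will be randomized to a calibrated formula intake intervention or control".
- Section 7.2.1: "following the visit, infants will be randomized to intervention or control using a computer-generated randomization program". The visit meant is Visit 1, which runs from birth to 1 month. No minimum age or interval after the visit is given.

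Visit 1 can be the hospital stay: "if enrollment occurs during the birth hospitalization, birth weight and birth length will be recorded from the electronic medical record". Section 15.1 expects recruitment and enrolment to be frequent on the maternity unit.

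On checking eligibility, 7.2 says: "Prior to enrollment, infants will be screened by study coordinators to ensure eligibility consistent with study inclusion/exclusion criteria". Section 4.1 adds that candidates are identified "via review of birth hospitalization and neonatal electronic medical records".

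The intervention begins later. Section 3.1 item 7 speaks of exclusive formula feeding "by the start of the intervention period ~ 1 month after delivery", and 7.2.2 first gives out the handouts, videos and formula volumes at Visit 2 (days 24-41), which both arms attend.

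Removal under 3.3.1 is for failure-to-thrive (two growth-chart definitions) or for missing two intervention visits. Under 3.3.2, withdrawn infants have no further data collected and are not replaced.

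**The concern.** An infant enrolled and randomised in hospital, or at a clinic visit before day 21, cannot have been screened against the one exclusion criterion. The pre-enrolment screening promised in 7.2 is impossible for that infant.

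If the infant is later found to be below birthweight at day 21, staff have two choices and no instruction. They can remove the infant, who is then lost from the 6-month outcome and not replaced, or keep an infant whom 3.2 calls ineligible. Section 8.3 defines no analysis population that would settle it.

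Three features make a rule worth having even if few infants are affected. The criterion reflects early weight gain, and the primary endpoint is conditional weight gain from birth to 6 months (1.2), so the decision selects on something tied to the outcome. Study coordinators both screen for eligibility (7.2) and give the feeding recommendations (7.2.2), and nothing says that a late eligibility decision is made without knowledge of the arm. Retention and visit completion are feasibility endpoints (1.3), and avoidable removals would blur them.

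**Working it through.** **Timeline.** Inputs are the day-21 criterion (3.2), the randomisation windows (1.1, 7.1, 7.2.1) and the Visit 2 window (7.2.2). One month is taken as day 30.

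| Window | Days before day 21 |
|---|---|
| Birth to 1 month, days 0-30 (7.1, 7.2.1) | 21 of 31 (68%) |
| 2-3 weeks read as days 14-21 (1.1) | 7 of 8 (88%) |
| 2-3 weeks read as completed weeks, days 14-27 (1.1) | 7 of 14 (50%) |

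Every stated window opens before the criterion can be assessed. These are shares of calendar days, not of infants; the documents give no distribution of age at randomisation.

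**Which weight would be used.** After hospital enrolment the next scheduled study weight is at Visit 2, which opens 24 - 21 = 3 days after the criterion becomes assessable and closes on day 41. The medical record may hold a clinic weight near day 21, but the plan neither schedules nor names one.

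**How many infants.** The plan gives no failure rate, so f is assumed to be 1%, 2% or 5%. With n infants randomised before day 21, the expected number failing is n × f, and the chance of at least one is 1 - (1 - f)^n.

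| n randomised early | f = 1% | f = 2% | f = 5% |
|---|---|---|---|
| 60 (all; upper bound) | 0.6 (45%) | 1.2 (70%) | 3.0 (95%) |
| 30 (half) | 0.3 (26%) | 0.6 (45%) | 1.5 (79%) |

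**Cost in precision.** If k of 60 are lost, intervals widen by √(60/(60 - k)) - 1. For k = 1 this is √(60/59) - 1 = 0.8%; for k = 3 it is √(60/57) - 1 = 2.6%.

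**Consents needed to randomise 60 after the check.** 60/(1 - f), rounded up: 60/0.99 gives 61, 60/0.98 gives 62, 60/0.95 gives 64, before any other early loss.

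**Separate precision gain.** Section 8.3 compares 6-month weight-for-length by ANOVA with no baseline covariate. Adjusting for the Visit 2 weight-for-length z-score multiplies the residual variance by about (1 - r²) × 58/57. The correlation r is not in the documents. For an assumed r = 0.3 the factor is 0.91 × 58/57 = 0.93, and for r = 0.5 it is 0.75 × 58/57 = 0.76. Taking square roots, intervals are about 4% to 13% narrower.

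**The case against.** A compatible reading exists. The one specific time, in 1.1, can end on day 21, and 7.2.1 sets no interval after the visit. Consent in hospital followed by randomisation at about day 21 would fit both. On that reading the fault is unreconciled wording rather than a chosen design. This is fair, but no section requires the later time, and the pre-enrolment screening in 7.2 still cannot be met for an infant enrolled in hospital.

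The gap in the removal rules may be narrower than it looks. An infant still below birthweight at day 21 has gained nothing, while the table in 7.2.2 gives month-1 velocities of 35.2 g/day for boys and 28.3 g/day for girls. Over 21 days the shortfall is 21 × 35.2 = 739 g or 21 × 28.3 = 594 g. Some such infants might also meet the centile-crossing definition in 3.3.1, for which 3.3.2 gives handling. That is a different measure, and the overlap cannot be computed from the documents, so the question stays open for the rest.

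The numbers are also likely to be small. Section 3.1 item 3 already keeps out infants with morbidity affecting feeding or weight gain, nothing in the documents supports the 5% rate, and all 60 randomised early is an upper bound. The trial is a pilot sized on feasibility, with no power claim (8.2). All of this stands and limits the severity.

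A reader might infer that the treatment comparison is biased. The documents do not support that: the intervention starts at Visit 2, and removal applied alike in both arms before allocation is known would not bias it. What can be said is that the plan does not state those conditions. A reader might also take 68% as the share of infants affected, which it is not.

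**Conclusion.** The conflict in the text is certain. A criterion that needs day 21 sits beside three statements that allow earlier randomisation and a screening step that early enrolees cannot pass through. The plan does not say whether a randomised infant who then fails is kept, withdrawn or analysed.

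The consequence is minor to moderate: avoidable loss after randomisation and case-by-case eligibility decisions in a 60-infant pilot. On the assumed rates of 1% to 5%, between 0.3 and 3.0 infants would be affected, depending also on whether half or all are randomised early. The true rate and the age distribution at randomisation are unknown. It is worth correcting because the remedy is mostly wording.

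**What to change.** **Timing.** Obtain consent at Visit 1. Randomise at Visit 2, after the criterion has been verified and before any intervention material is given. Allow earlier randomisation only where a weight at or after day 21 is already on record. Make 1.1, 7.1, 7.2 and 7.2.1 give this one time point.

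**The criterion.** No study weight is scheduled at day 21, and a weight above birthweight on day 41 does not show the infant's status at day 21. Reconcile the wording of 3.2 with the weight actually used, naming its source and day window.

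**Consequential wording.**

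- State that the age limit of 1 month (3.1 item 4) applies at consent, since Visit 2 can fall as late as day 41.
- State that 60 (8.1) means randomised infants.
- Say how 3.3.1 item 2 counts the 1-month visit.
- Report consented infants who fail or are lost before randomisation separately, so that these losses stay visible in the feasibility results.

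**If earlier randomisation is kept.** State that infants who then fail the criterion are followed and analysed in their randomised arm.

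**Cost.** No visit is added, but allocation must fit within a visit described in 7.3 as adding about 15 minutes. Slightly more than 60 consents are needed: about 61 to 64 at the assumed rates, plus other early losses. Section 15.2 expects 200-300 eligible infants a year, or 100-150 in the 6-month recruitment period of 8.1.

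**A separate free improvement, which does not cure the timing defect.** Adjust the 6-month weight-for-length comparison for the Visit 2 weight-for-length z-score, which is measured in both arms before the intervention starts. Keep an infant who lacks that measurement in the analysis by a simple baseline imputation, such as the mean over both arms. The data are already collected; the size of the gain depends on the assumed correlation.

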1.2 Primary Study Endpoints

State the primary endpoints to be measured in the study.

Clinical trials typically have a primary objective or endpoint. Additional objectives and endpoints are secondary. The endpoints (or outcomes), determined for each study subject, are the quantitative measurements required by the objectives. Measuring the selected endpoints is the goal of a trial (examples: response rate and survival).

- Conditional Weight Gain between Birth and Age 6 months

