8.0 Number of Subjects and Statistical Plan

8.1 Number of Subjects

Indicate the maximum number of subjects to be accrued/enrolled. Distinguish between the number of subjects who are expected to be enrolled and screened, and the number of subjects needed to complete the research procedures if applicable (i.e., numbers of subjects excluding screen failures.)

For this pilot study, 60 infants will be recruited. We believe that this number of infants who meet the inclusion/exclusion criteria can feasibly be recruited over a 6 month period.

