8.2 Sample size determination

If applicable, provide a justification of the sample size outlined in section 8.1 to include reflections on, or calculations of, the power of the study.

The sample size for this pilot study is based upon the number of participants that we felt we could feasibly recruit given the time and resources available for recruitment. As this pilot is going to determine feasibility, 60 participants should be adequate. Further, we will use the data generated to determine the sample size necessary for a fully powered subsequent trial.

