8.3 Statistical methods

Describe the statistical methods (or non-statistical methods of analysis) that will be employed.

We will assess conditional weight gain from birth to 6 months to assess rapid infant growth.^{80,81} Conditional weight gain will be calculated as standardized residuals from the linear regression of weight for age at 6 months on weight for age at birth, with length for age at birth and 6 months and infant age at the 6-month visit entered as covariates. We will explore the moderating role of child sex, delivery mode, and maternal parity on intervention effects. Similar analyses will be conducted for the intervention period spanning ages 1-6 months.

For cross-sectional analyses at age 6 months, ANOVA will estimate the effects of intervention group on mean weight-for-length. Logistic regression will be used to compare intervention effects on the dichotomous outcome of overweight at 6 months.

For growth from 1-6 months, we will fit a repeated measures ANOVA of BMI, with visit and study group as within and between factors, respectively.

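### Randomisation is stratified by infant sex and maternal BMI category, but no main between-arm comparison in section 8.3 is stated to include them

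*Combined protocol and SAP*

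**What the plan says.** Section 7.2.1 (Visit 1, Randomization) describes the allocation: "infants will be randomized to intervention or control using a computer-generated randomization program generated by a statistician not affiliated with the trial". It then adds: "Randomization will include stratification for sex of the infant (male/female) and maternal pre-pregnancy BMI category". The BMI categories are 25-29.9 and 30 or more, so there are four strata. No block size, minimisation rule or allocation ratio is given.

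Section 8.1 sets the size: "For this pilot study, 60 infants will be recruited". Section 8.2 gives the reason: "The sample size for this pilot study is based upon the number of participants that we felt we could feasibly recruit". No significance level, power, effect size or standard deviation is stated.

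Section 8.3 is the whole analysis plan. On the two stratification factors it reads as follows:

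- **Primary outcome** (section 1.2, "Conditional Weight Gain between Birth and Age 6 months"). It is a residual from a regression of 6-month on birth weight-for-age, "with length for age at birth and 6 months and infant age at the 6-month visit entered as covariates". Neither factor is named. The model that then compares the arms on this residual is not written out.
- **Moderators.** "We will explore the moderating role of child sex, delivery mode, and maternal parity on intervention effects". Sex is included here. Maternal BMI category is not.
- **Conditional gain from 1 to 6 months.** Analysed in a similar way.
- **6-month weight-for-length.** ANOVA on group, with no other term named.
- **Overweight at 6 months.** Logistic regression, with no covariates named.
- **Growth from 1 to 6 months.** Repeated measures ANOVA, "with visit and study group as within and between factors, respectively".

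**The concern.** Allocation that balances the arms within strata removes between-stratum variation from the arm contrast. A model without the strata still counts that variation as residual error. The contrast is then more precise than its reported standard error shows: intervals are too wide and tests run below their nominal level.

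Section 2.1 treats maternal overweight and obesity as a driver of infant weight gain, and 7.2.1 judges BMI category worth stratifying on. Section 8.3 then never mentions it.

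Two things are at stake in a 60-infant pilot. First, the estimates are meant to size the next trial (8.2), so the stated uncertainty should match the design. If that trial adjusts for these factors, sizing it from the unadjusted variance multiplies its sample size by 1/(1 − R²). That is 1.05, 1.11 or 1.25 at R² of 0.05, 0.10 or 0.20. Second, because 8.3 is silent, the choice between adjusted and unadjusted results could be made after the data are seen.

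**Working it through.** There is no figure in the plan to reproduce, since the sample size rests on feasibility alone. The check is of how much the omission could matter.

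**Inputs from the documents:** N = 60 (8.1); two binary stratification factors (7.2.1).

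**Assumptions:** 1:1 allocation; each factor split 50/50; outcome SD 1; two-sided 5% test; R² (share of outcome variance explained by the strata) from 0 to 0.20. Two allocation schemes were tried: permuted blocks of 4 within strata, and no blocking.

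**Formulas, allocation balanced within strata.** The true SE of the arm difference is the unadjusted reported SE times √(1 − R²). So:

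- ratio of reported to true SE = 1/√(1 − R²)
- actual level = 2[1 − Φ(1.96/√(1 − R²))]

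| R² | √(1 − R²) | Interval too wide by | 1.96/√(1 − R²) | Actual level |
|---|---|---|---|---|
| 0 | 1 | 0% | 1.960 | 0.050 |
| 0.05 | 0.975 | 2.6% | 2.011 | 0.044 |
| 0.10 | 0.949 | 5.4% | 2.066 | 0.039 |
| 0.20 | 0.894 | 11.8% | 2.191 | 0.028 |

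**Simulation, blocks of 4** (8,000 trials per row, R² shared equally between the factors; power is for an illustrative 0.5 SD effect):

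| R² | True SD of unadjusted estimate | Reported SE, unadjusted | Level, unadjusted | Reported SE, adjusted | Level, adjusted | Power, unadjusted to adjusted |
|---|---|---|---|---|---|---|
| 0 | 0.2544 | 0.2570 | 0.0450 | 0.2573 | 0.0445 | 0.477 to 0.474 |
| 0.02 | 0.2567 | 0.2571 | 0.0496 | 0.2545 | 0.0520 | 0.479 to 0.486 |
| 0.05 | 0.2556 | 0.2579 | 0.0491 | 0.2513 | 0.0529 | 0.476 to 0.493 |
| 0.10 | 0.2430 | 0.2574 | 0.0385 | 0.2442 | 0.0506 | 0.480 to 0.522 |
| 0.20 | 0.2311 | 0.2577 | 0.0285 | 0.2302 | 0.0476 | 0.481 to 0.572 |

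The unadjusted reported SE exceeds the true SD by 0.2574/0.2430 − 1 = 5.9% at R² = 0.10 and by 0.2577/0.2311 − 1 = 11.5% at 0.20. At R² of 0.05 or less the excess is about 1% or under. Simulation error is √(0.05 × 0.95/8000) = 0.0024 on a level and about 1/√(2 × 8000) = 0.8% on an SD, so the small-R² rows cannot be told apart from no effect.

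A separate run put all the explained variance on BMI category (20,000 trials per R²). It gave unadjusted levels of 0.0441, 0.0386 and 0.0288, and adjusted levels of 0.0495, 0.0493 and 0.0487, at R² of 0.05, 0.10 and 0.20. This agrees with the formula.

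**Simulation, no blocking.** At R² = 0.20 the true SD is 0.2612, the reported unadjusted SE 0.2595 and the level 0.0509, so the unadjusted analysis is correct. Adjustment lowers the SE to 0.2361 and raises power from 0.462 to 0.543. At R² = 0 it raises the SE from 0.2591 to 0.2636, and power goes from 0.476 to 0.465.

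**Scope.** These figures are for a linear model with one measurement per infant. In the repeated measures model they carry over to the group contrast averaged over visits, not automatically to the group-by-visit term.

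**The case against.** The strongest reply is that the size of the effect rests on two quantities the documents do not give.

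- **Blocking.** Section 7.2.1 does not say how balance within strata is achieved. If it is not achieved, the unadjusted standard error is right. This stands.
- **R².** With two equal groups, R² of 0.05, 0.10 and 0.20 on BMI category alone implies differences of 2√R² = 0.45, 0.63 and 0.89 SD between infants of overweight and of obese mothers. The upper values look large. Every mother has BMI of at least 25 and every infant a birthweight at or above the 50th percentile (3.1), so the range is already restricted. The primary outcome is also conditioned on birth size and on length and age at 6 months. Values near 0 to 0.05 cannot be excluded. This stands.
- **Sex.** If weight and length are scored on sex-specific standards, sex should explain little; 8.3 does not say which standard is used. BMI in the trajectory model is not described as sex-standardised.
- **Consequence.** Any error is conservative, and no stated power claim is undermined.

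A reader might also infer more than the documents support:

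- That no planned analysis uses the strata. Sex is an exploratory moderator in 8.3, and a sex-by-group model would normally contain sex as a main effect. That is still not an adjustment of the main comparison.
- That the balance gained by stratifying is lost. Balance comes from the allocation and remains whatever model is fitted; only precision and the exact test level are affected.
- That the standard errors are too large as a matter of fact. This holds only under the two conditions above.
- That the primary comparison is specified without the strata. Its between-arm model is not specified at all.
- That the same argument covers the logistic model. Adding prognostic covariates there does not generally shrink the standard error of the log odds ratio.

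What remains is that the plan does not say whether its main comparisons follow its own stratification.

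**Conclusion.** The point holds as an omission with a limited and conservative effect. No main between-arm comparison in 8.3 is stated to include the factors used in randomisation, and maternal BMI category is used in no analysis.

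For continuous outcomes, if allocation is balanced within strata and R² lies between 0 and 0.20 (both assumed), intervals are about 0 to 12% too wide and the actual test level runs from about 5% down to about 3%. At R² of 0.05 or less the effect is negligible (under 3% on interval width). Without effective blocking there is no error in the unadjusted standard error, only a forgone precision gain. In no case is type I error inflated or the estimate biased.

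This is a worthwhile improvement at almost no cost. It does not threaten the pilot's conclusions.

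**What to change.** Add to section 8.3: *Between-arm models for continuous outcomes (conditional weight gain, 6-month weight-for-length Z-score, 1-6 month trajectory) will include infant sex and maternal pre-pregnancy BMI category, as used in randomisation, as fixed effects.* For conditional weight gain, this also means writing down the model that compares the arms. Leave the binary overweight outcome out of the rule: it is sparse, and the precision argument does not carry over to it.

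The cost is one sentence and two degrees of freedom. Both variables are known at randomisation. If the strata turn out not to be prognostic, the loss is negligible: at an illustrative 0.5 SD effect, simulated power moves from 0.477 to 0.474 with blocking and from 0.476 to 0.465 without. Infants withdrawn under 3.3 contribute no further data and are not replaced, so the adjustment also guards against stratum imbalance arising in the analysed set.
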